Random schedule of testing with progressive decrease in frequency of testing. To ensure that Incentive participants do not wait to take their antiretroviral medications consistently in the month before a viral load test, viral load blood tests will be scheduled at random times throughout the 2-year intervention evaluation period. At each viral load blood test, if the participant provides a blood sample that meets the criteria for earning an incentive (e.g., an undetectable viral load or a decrease in viral load of 0.15 log per week since the last blood sample provided), the participant will earn an incentive equal to \$10 per day for all the days since the last blood test. For example, if two weeks had passed since the last viral load test, the participant would earn \$140 for providing a blood sample with an undetectable viral load (\$10 per day X 14 days = \$140). Initially, the viral load blood tests will occur once every week. Once the participant provides blood samples with sufficiently decreased or undetectable viral loads on 4 consecutive weekly blood tests, the inter-test interval will be increased to once every 2 weeks, on average. Once the participant provides blood samples with sufficiently decreased or undetectable viral loads on 2 consecutive blood tests, the inter-test interval will be increased to once every 4 weeks, on average. Once the participant provides blood samples with sufficiently decreased or undetectable viral loads on 2 consecutive blood tests at that inter-test interval, the inter-test interval will be increased to 8 weeks, on average. Once the participant provides blood samples with sufficiently decreased or undetectable viral loads on 2 consecutive blood tests at that inter-test interval, the inter-test interval will be increased to 12 weeks, on average. The inter-test interval will remain at 12 weeks for the remainder of the 2-year intervention evaluation period, which is equivalent to the standard inter-test interval for viral load testing under standard care (Panel on Antiretroviral Guidelines for Adults and Adolescents, 2013). Each participant will call the Incentive Program every Monday to determine if they are scheduled to provide a blood sample that week. To ensure that participants call every week, participants will be paid \$5 for each weekly call. If a blood sample is scheduled for that week, the participant will schedule a time for the collection within that week (Monday-Friday).

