Reloadable credit card. At the start of each participant's enrollment, each participant will be given a reloadable credit card. When the participant calls to get the results of a given viral load test, the Incentive staff will tell the participant the results. If the participant met the criterion for the incentive, the Incentive staff will tell the participant the amount of the incentive earned and add the incentive amount to the participant's reloadable credit card. This procedure will ensure that participants monitor the results of their viral load testing and know when, why and how much is added to their credit card. That card can then be used as a regular credit card to make purchases at most businesses. We currently use this reloadable credit card system in our Therapeutic Workplace incentive program, and it has proved very efficient and highly acceptable to participants.

Usual Care Control Group

Usual Care Control Only participants will receive the standard HIV medical care described above offered in their medical clinic. Participants in this group will not receive added viral load testing, feedback or incentives, beyond the viral load testing conducted as a routine part of their medical care.

Assessments

For all participants, assessments will be conducted at intake to determine eligibility and characterize participants. Outcome assessments will be conducted at intake, every 3 months throughout the 2-year intervention evaluation and every 6 months of the 1-year follow-up period. Except for the computerized delay discounting task, the assessments will be administered using the Qualtrics web-based software (<http://qualtrics.com/>) to administer and record responses for the questionnaires administered under this protocol. When necessary (e.g., if the web server is not operational), a printed version of the questions will be used.

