visual analog scale (VAS) to assess ART adherence in which participants mark a 100 mm line to indicate their percent adherence to their antiretroviral medications over the previous 4 weeks (Buscher et al., 2011; Walsh et al., 2002). Responses on this VAS have been associated with pill taking with MEMS (Buscher et al., 2011; Walsh et al., 2002), pill count (Walsh et al., 2002), and pharmacy records (Buscher et al., 2011). 7) Assess whether each participant refilled their ART prescription for each month, the pharmacy that filled each prescription, and the medication. 8) Pharmacy records will be obtained (with participant permission) to confirm self-reported data. 9) Participants will be asked how many primary HIV care visits they had in the past 3 months using procedures and definitions used in a prior multisite study (Purcell et al., 2007). Medical records will be obtained with permission to confirm self-reports. 10) The *Modified Economic Form 90 AIR/ED* will be created for this study based on the Economic Form 90 AIR/ED (Bray et al., 2007; Miller and Del Boca, 1994; Scheurich et al., 2005; Tonigan et al., 1997) to collect patient data on all health care utilization within the past 180 days. 10) A Modified SASCAP (Zarkin, Dunlap et al. 2004) will be used to estimate the costs associated with services in the study conditions. The SASCAP (www.rti.org/sascap) assesses activity-level resource use and cost data for intervention staff, consultants, and non-labor resources (e.g., building space) used in the provision of intervention services. The SASCAP method reliably estimates the costs of intervention activities and the cost per participant. Zarkin and Dunlap have applied this micro-costing approach (Zarkin et al., 2003, 2005, 2008, 2010; Dunlap et al., 2010). 11) A multiple-choice test evaluating the HIV Education Course.

b. Study duration and number of study visits required of research participants.

Participants in the incentive group will receive the incentive intervention for two years. For all participants, assessments will be conducted at intake to determine eligibility and characterize participants. Outcome assessments will be conducted at intake, every 3 months throughout the 2-year intervention evaluation and every 6 months of the 1-year follow-up period.

c. Blinding, including justification for blinding or not blinding the trial, if applicable.

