The primary outcome measure of undetectable viral loads will be analyzed with a longitudinal logistic regression model using GEE (Diggle & Diggle, 2002). We used Liu and Liang (1997) to determine the total N required to detect a difference between groups with 80% power. The adjacent figure shows the total number of participants (N) required to detect a difference of 15% between the Usual Care Control and the Incentive Group at the eight 3-month assessments during the intervention evaluation period. The figure shows different percentages for the Usual Care Control group because that value affects the sample size required. 15% is smaller than the effects produced in all prior studies of voucher reinforcement of cocaine or opiate abstinence or medication adherence and smaller than all effects produced by the Therapeutic Workplace and smaller than the incentive effects in promoting drug abstinence, medication adherence and other health behaviors as shown in three different meta-analyses (Petry et al., 2012; Prendergast et al. 2006; Lussier et al., 2006). The horizontal red lines show the number of participants planned based on the number of participants enrolled and randomized to the two groups without (top dashed line) and after adjusting for the anticipated rates of missing data (20% missing, bottom solid red line). Based on this analysis, we need to enroll and randomize 200 participants (horizontal dashed line) to ensure that we have sufficient sample sizes after adjusting for the rates of missing data. After adjusting for missing data (20% missing), this would yield a sample size of 160 participants (200 participants x 0.80 collected samples = 160 participants). The adjusted sample size of 160 participants (solid red line) is a little more than the maximum number of participants that would be required.

c. Early stopping rules.

The protocol can be stopped based on recommendations of the Scientific Advisory Committee overseeing this study. We will ask the Scientific Advisory Committee to recommend that the trial be stopped if a review of the adverse events suggests to any of the investigators that the number of related and unexpected adverse events is unacceptably high. The Scientific Advisory Committee will be allowed to request statistical analyses to compare the groups on the rates of different adverse events or to have the adverse event data summarized in other ways that they deem appropriate.

Risks

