Unanticipated problems or study deviations will be reported based on the guidelines of the Johns Hopkins University School of Medicine IRB.

d. Legal risks such as the risks that would be associated with breach of confidentiality.

There are risks that the confidential information we collect could be revealed to people not involved in the research such as a friend, relative, or an outside organization. This could be embarrassing to the participant if the participant wanted to keep participation in the study secret. The legal risks are limited because we collect only general information about participant activities, legal and illegal. We do not collect information about specific illegal acts. Thus, the risks associated with the assessments are not greater than the risks associated with routine psychological examinations or tests.

e. Financial risks to the participants.

There are no financial risks above those of normal daily living. Each participant is responsible for ensuring that the earnings are reported properly to relevant government or private agencies and for determining whether or not the earnings will affect any benefits they might receive from those agencies.

8. Benefits

a. Description of the probable benefits for the participant and for society.

Participants in the incentive group will receive incentives for maintaining undetectable viral loads. The incentive payments could substantially increase adherence to antiretroviral medications and thereby increase the percentage of patients that achieve undetectable viral loads. That could improve the long-term health of participants.

This novel incentive intervention being developed in this project could be an effective and economically sound means of promoting long-term adherence to antiretroviral medications and suppression of viral load in adults living with HIV. If the intervention is effective and economically sound, it could be used widely to promote suppression of viral load in adults living with HIV. The intervention could benefit those HIV-infected individuals by improving their long-term health. Importantly, if the incentive intervention is effective in suppressing viral load, it could dramatically reduce the transmission of HIV to others in the community.

9. Payment and Remuneration

a. Detail compensation for participants including possible total compensation, proposed bonus, and any proposed reductions or penalties for not completing the protocol.

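### The plan allows a between-group comparison of adverse event rates but names no common source for adverse events, while scheduled contact differs widely by arm, so ascertainment could differ

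*Combined protocol and SAP*

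**What the plan says.** Section 7c (Early stopping rules) ties a request for a stop recommendation to a review of adverse events suggesting, to any investigator, that "the number of related and unexpected adverse events is unacceptably high". It then lets the Scientific Advisory Committee "request statistical analyses to compare the groups on the rates of different adverse events". The committee may also have the data summarised in other ways. No other between-arm safety analysis appears in the plan.

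Section 4a (Assessments) sets one schedule for both arms: intake, then "every 3 months throughout the 2-year intervention evaluation and every 6 months of the 1-year follow-up period". The itemised list covers viral load, drug assays, CD4, urine tests, an adherence scale, refills and pharmacy records, care visits, a modified Economic Form 90, a modified SASCAP and an education test. It has no adverse event item. The Form 90 is there to "collect patient data on all health care utilization within the past 180 days" and is used for the economic analyses. The list is introduced as assessments that may be done at all time points.

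On reporting, the Risks section (item c) says only: "Unanticipated problems or study deviations will be reported based on the guidelines of the Johns Hopkins University School of Medicine IRB".

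On contact, section 4a says for the Incentive group: "Each participant will call the Incentive Program every Monday". That group also has randomly timed blood tests and a call for each result. For controls: "Participants in this group will not receive added viral load testing, feedback or incentives". Participants are unblinded (section 4c).

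**The concern.** A comparison of event rates is interpretable only if an event has the same chance of being recorded in each arm. The plan foresees the comparison but does not say how events come to be recorded. If the practice is to note whatever participants mention when they are in touch with staff, the arm with more contact will tend to show more events.

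The committee could then see an excess in the Incentive arm and be unable to tell three things apart: chance, fuller recording, and real harm from the extra blood draws. The comparison is made on request and can use only data already collected, so a gap in collection cannot be repaired by later analysis. The primary outcome and its analysis are not affected.

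**Working it through.** The plan gives no adverse event rate and no contact count, so there is no stated figure to reproduce. The contact counts below are built from section 4a.

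**Inputs (2-year intervention period)**
- Common assessments: every 3 months, so 8 in each arm.
- Monday calls, Incentive only: 52 × 2 = 104.
- Incentive blood tests if every test meets the criterion: 4 weekly (4 weeks), 2 at 2 weeks (4 weeks), 2 at 4 weeks (8 weeks) and 2 at 8 weeks (16 weeks) make 10 tests in 32 weeks. The rest is (104 − 32)/12 = 6. Total 10 + 6 = 16. Intervals beyond the weekly stage are averages, so 16 is an expected schedule.
- Most frequent testing: one per week (Risks, item a), so up to about 104.

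**Scheduled contacts per participant**

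| Counting rule | Incentive | Control | Ratio |
|---|---|---|---|
| Calls + 16 draws + assessments | 104 + 16 + 8 = 128 | 8 | 16 |
| Same, result calls counted separately | 128 + 16 = 144 | 8 | 18 |
| Weekly draws throughout | 104 + 104 + 8 = 216 | 8 | 27 |
| Draws merged with calls | 104 + 8 = 112 | 8 | 14 |
| First row, plus intake and follow-up year | 128 + 3 = 131 | 8 + 3 = 11 | 11.9 |
| In person, 16 draws | 16 + 8 = 24 | 8 | 3 |
| In person, weekly draws | 104 + 8 = 112 | 8 | 14 |

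The ratio depends on the counting rule, but for a participant active in the programme none of these rules gives parity.

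**What unequal recording would do (illustration only)**

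The values here are assumed; they are neither in the documents nor derived from the contact ratio. Take 100 participants per arm, equal true rates of 0.25 to 1.0 events per person, and 50% of events recorded in Control. With counts a (Control) and b (Incentive), the test is z = (b − a)/√(a + b), declared a significant Incentive excess if z > 1.96. The apparent rate ratio is simply the ratio of the recording proportions.

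| Recorded in Incentive | Apparent rate ratio | Chance of a false significant excess |
|---|---|---|
| 50% | 1.0 | 2.4–2.6% |
| 60% | 1.2 | 7–16% |
| 75% | 1.5 | 20–61% |
| 100% | 2.0 | 54–99% |

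The chances come from simulated Poisson counts. A hand check at 0.5 events per person and 75% recording: expected counts are 25 and 37.5, so z centres on 12.5/√62.5 = 1.58, and the chance of exceeding 1.96 is about 35%. The simulation also gives 35%.

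**Look-back overlap of the Form 90**

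The look-back is 180 days and assessments are about 365/4 ≈ 91 days apart, so consecutive forms overlap by about 180 − 91 = 89 days. Without matching by date, one hospitalisation could be counted twice.

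**The case against.** The strongest reply is that bias is not demonstrated. A reader might infer from the contact counts that the comparison is biased against the incentives. The documents do not support that. The Monday call is described as finding out whether a sample is due, and the result call as giving the result and the payment. Nothing says events are asked about or recorded at either, or at draws. Silence about method does not establish unequal method. This stands, and the point is therefore limited to ascertainment that could differ.

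Four further stronger readings also fail:

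- *That the comparison drives stopping.* It is optional, and the stated trigger is the number of related and unexpected events, not a group difference.
- *That 16-fold is a minimum.* It is a count of scheduled contacts dominated by brief calls. The in-person ratio for a participant who always meets the criterion is 3. Draws and the programme start only once a medication bottle is shown, so actual contact can be lower.
- *That nothing common to both arms captures events.* The Form 90 and medical records would pick up events that led to care. They are simply not designated for adverse events.
- *That any Incentive excess would be spurious.* The Risks section lists bruising, fainting and infection from blood draws, and this arm has about 16 to 104 more of them. Some excess could be real.

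It is also fair to say that the plan describes little risk beyond daily life, that adverse events are not an endpoint, and that the text available is incomplete. It cites a section 13.7 that we do not have, though only for a recruitment letter. An adverse event procedure elsewhere cannot be ruled out.

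What remains is that the both-arm assessments are itemised without an adverse event question, while a comparison of rates is expressly allowed and contact is unequal by design.

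**Conclusion.** The point holds in limited form. As written, the plan permits a between-group comparison of adverse event rates without a designated common source. Scheduled contact over 2 years is about 16 to 1 (128 against 8), or about 3 to 1 in person (24 against 8), for an Incentive participant who always meets the criterion. More recorded events in the Incentive arm is the plausible direction if spontaneous reports are noted at any contact. The size is unknown, and the false-excess figures only show what would follow from assumed recording proportions.

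The conclusion assumes that no adverse event form exists outside the text available. It is worth acting on because the gap cannot be repaired later and the remedy is small. It does not threaten the primary result.

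**What to change.** 1. Add one standard adverse event question, with a fixed look-back to the previous assessment, to the existing interview at each common 3- and 6-month assessment in both arms. It can also be asked by phone under the COVID-19 procedures.
2. Supplement it with hospitalisations and emergency visits from the Form 90, matched by date so that each event counts once. State that the question and the Form 90 will be given at every common assessment, not that they may be.
3. State that the main between-group rate comparison uses this common source only.
4. Tabulate events learned of at Incentive calls or draws separately by source, including blood-draw events, and report them in full to the committee. Leaving them out of view would hide real procedure harms that fall mainly on this arm.
5. For assessments already completed, say that no standard question was asked and that the comparison rests on the Form 90 where it was collected.

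The cost is one interview question and a paragraph of protocol text. The downside is that some minor events forgotten between assessments will be lost from the main comparison; the separate table limits this for the Incentive arm. The stopping criterion itself is not changed.

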Feedback of the viral load tests. Participants will provide blood samples according to the schedule described below. Each sample will be tested for HIV-1 RNA (viral load) by a CLIA-certified outside laboratory. We should obtain the results of the viral load test within 1 week of the collection. Each participant will be instructed to call the Incentive Program staff to obtain the results of the viral load testing 1 week after the blood sample was collected. Incentives will be provided when the participant calls the Incentive Program staff for the results of viral load testing. If the viral load results are obtained by the time the participant calls in for the next blood draw (see below), the results will be provided to the participant at that time. With the patient's consent, the results will be forwarded to the patient's physician.

Providing incentives for decreased viral load. Throughout the intervention, participants will be able to earn up to \$10 per day for providing blood samples that have undetectable viral loads (i.e., <200 copies/mL) or viral loads that have decreased by 0.15 log per week since the last viral load assessed. This amount of decrease is based on research of the decay dynamics of viral load in response to ART. [name], a co-investigator on this grant application, is a world renowned expert on decay dynamics of viral load in response to ART. Research by [name] and others (Maldarelli et al., 2007; Perelson et

al. 1997; Sedaghat et al. 2008) shows that HIV-1 viremia decays in three stages in response to ART. HIV-1 viremia decays rapidly in the initial stage, with a half-life of as little as one day. That stage is relatively brief and lasts only a matter of days. In the second stage, HIV-1 viremia decays at a slower rate, with a half-life of about two weeks. The third stage occurs after viral load has fallen below the level detection by clinical assays, and is thus not relevant to the incentive intervention. Our criterion for incentives assumes: 1) patients will typically be in the second stage until their viral load reaches the undetectable threshold, and 2) HIV-1 viremia will always decay at a rate equal to or greater than the second stage (i.e., with a half-life of 2 weeks or shorter). We expect that viral load should decrease by at least 0.15 log per week until it is undetectable if the patient is taking ART consistently.

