a. Primary outcome variable.

Specific Aim. Assess the effectiveness of an empirically-based incentive intervention in maintaining undetectable viral loads in people living with HIV. We will assess the percentage of blood samples that have undetectable viral loads (i.e., <200 copies/mL) at the eight 3-month assessments conducted throughout the 2-year intervention evaluation period (Y/N at each assessment).

a. Secondary outcome variables.

We expect that the incentive intervention could affect measures that are not directly targeted by the intervention. Since patients must adhere to ART and stay in HIV care to achieve undetectable levels of viral load, we expect that the incentive intervention will increase consistent adherence to ART, maintenance of prescriptions for ART, and retention in HIV medical care. It may also produce post-intervention effects.

Specific Aim. Assess the effectiveness of an empirically-based incentive intervention for decreased or undetectable viral loads in promoting biologically-verified adherence to antiretroviral medications. We will assess whether the participant maintained consistent ART adherence by conducting qualitative high-resolution mass spectrometry (HRMS) blood tests of 15 antiretroviral medications. Participants will be considered adherent if they test positive for all of their prescribed medications (Y/N at each 3-month assessment).

Specific Aim. Assess the effectiveness of an empirically-based incentive intervention for decreased or undetectable viral loads in promoting self-reported adherence to antiretroviral medications. We will assess whether the participant reports maintaining consistent ART adherence by reporting taking >90% of all scheduled doses in the past 30 days (Y/N at each 3-month assessment based on responses on a visual analog scale to assess adherence to antiretroviral medications, see below).

Specific Aim. Assess the effectiveness of an empirically-based incentive intervention for decreased or undetectable viral loads in maintaining prescriptions for antiretroviral medications. We will assess the percentage of months that the participant refilled a prescription for antiretroviral medications throughout the 2-year intervention evaluation period (Y/N for each month prior to each 3-month assessment based on timeline follow-back self-report and confirmed by pharmacy records).

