Mediation analysis. We will assess potential mediating effects of medication adherence as assessed by qualitative blood testing on viral load using the method of Baron and Kenny (1986). Specifically, this involves estimation of (1) the effect of treatment assignment (incentives) on undetectable viral load without controlling for medication adherence, (2) the direct effect of incentives on medication adherence, and if these two steps yield clinically and statistically significant effects, 3) the effect of incentives on viral load after controlling for medication adherence ($\text{logit } (Y_{ij}) = \beta_0 + \beta_1 x_i + \beta_{2-6} x_{2-6} + \beta_7 \text{adherence} + \epsilon_{ij}$). If medication adherence does mediate the effect of the incentives on presence of a detectable viral load, in this final model we would expect the effect of treatment (β_1) to be attenuated relative to the step 1 model, and for adherence (β_7) to be a clinically and statistically significant predictor of presence of a detectable viral load.

Missing data. We expect to collect $\geq 80\%$ of 3-month assessments (see below). Our primary approach will be to impute all missing values as the adverse outcome (e.g., detectable viral load). Model parameter estimates from this approach will be compared to a method without imputation. If these methods yield differing results, conclusions will need to be tentative. To investigate sensitivity to missing values, participants with and without missing values will be compared by covariates and treatment assignment.

ECONOMIC ANALYSES

We will use the provider perspective using a modified SASCAP and the research team's financial records. Intervention activities will be captured with the modified Economic Form 90 AIR/ED.

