a. Medical risks, listing all procedures, their major and minor risks and expected frequency.

There is essentially no risk above those of normal daily living associated with the incentives, or with the data collection procedures used in these studies.

Blood samples will be collected from participants in the Incentive group. Those participants will provide a maximum of 1 blood sample per week. The samples will be tested for viral load and will involve collecting up to 10 cc of blood per sample. Participants in both groups will provide blood samples every 3 months for the primary and secondary outcome measures. Each of those samples (25 cc in total) will be tested for viral load (10 cc), for the presence of antiretroviral medications (5 cc), and for CD4 Counts (10 cc). Taking blood may cause some discomfort, bleeding or bruising where the needle enters the body, and in rare cases, it may result in fainting. There is a small risk of infection. When possible, we will use data available in each participant's medical records to get recent viral load and CD4 counts measures instead of collecting blood samples at each assessment time point.

b. Steps taken to minimize the risks.

To protect confidentiality, all research participants are identified by participant identification codes (Participant IDs) consisting of their initials and sequentially-assigned participant numbers on most forms and data files, and not by their names. Picture ID cards are maintained by staff in a locked container, and kept in a locked, secured area when not in use. All research data are stored in locked areas accessible only to research staff and are not left unattended. Documents with confidential information are shredded before being discarded. Confidential information is never given to anyone outside of the research program without the explicit written permission of the research participant. Only selected designated staff members are approved to give confidential information out after obtaining explicit written permission from the

participant. All research staff are trained in these procedures. We collect only general information about participant activities, legal and illegal. We do not collect information about specific illegal acts. To further protect confidentiality, we will obtain a confidentiality certificate from NIH to protect data collected in this study.

c. Plan for reporting unanticipated problems or study deviations.

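### HRMS adherence tests that are not drawn by design, because records or remote visits replace the study sample, would be scored as non-adherent

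*Combined protocol and SAP*

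**What the plan says.** Risks, a. Medical risks, sets the baseline plan: "Participants in both groups will provide blood samples every 3 months for the primary and secondary outcome measures". Each sample is 25 cc: 10 cc for viral load, 5 cc for antiretroviral drugs and 10 cc for CD4. The same paragraph ends by allowing the trial, when possible, to use medical records "to get recent viral load and CD4 counts measures instead of collecting blood samples at each assessment time point". It does not say whether the 5 cc drug tube is still taken when that happens.

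The COVID-19 Procedures in section 4a go further. All remaining assessments are to be done without in-person contact, with blood and urine results taken from the clinic where possible.

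Section 7, Secondary outcome variables, defines biologically verified adherence "by conducting qualitative high-resolution mass spectrometry (HRMS) blood tests of 15 antiretroviral medications", yes or no at each 3-month assessment. "Participants will be considered adherent if they test positive for all of their prescribed medications". No section names a clinic or record source for this test.

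Under Missing data in section 7b: "Our primary approach will be to impute all missing values as the adverse outcome". The example given is a detectable viral load, and no exception is made for a test that was not drawn by design. The paragraph adds: "Model parameter estimates from this approach will be compared to a method without imputation". If the two differ, conclusions are to be tentative. Participants with and without missing values are also to be compared by covariates and by arm.

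**The concern.** Scoring a missing value as adverse is a defensible convention when a participant fails to attend. It is hard to defend when the participant attended, or was interviewed by phone, and the trial itself took no HRMS sample. Such a value says nothing about drug taking, yet it would enter the analysis as evidence of non-adherence.

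At stake is the only biologically verified adherence outcome. The same variable is the mediator in the mediation analysis, which is not pursued here. The primary outcome is not made missing by this route, because the record that replaces the draw supplies the viral load.

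The loss could also differ between arms. The economic aims expect greater treatment engagement in the Incentive group. In addition, the viral load results from the incentive program go to the clinic: with the patient's "consent, the results will be forwarded to the" patient's physician. Both make fuller records in the Incentive arm plausible. Neither is quantified.

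**Working it through.** **The plan's own figure.** The Power Analysis allows for 20% missing data: 200 × 0.80 = 160, and 160 / 0.80 = 200. This reproduces. It concerns the primary outcome. The documents give no figure for HRMS missingness or for how often records replace a draw.

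**What each rule does to each test.**

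| Test | Record or clinic source named | If no study sample is drawn |
|---|---|---|
| Viral load (10 cc) | Yes | Value taken from record |
| CD4 (10 cc) | Yes | Value taken from record |
| HRMS (5 cc) | No | Missing, then scored non-adherent |

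**Effect on the difference.** Inputs, all assumed: true adherence 70% (Incentive) and 55% (Usual Care), and a share *s* of HRMS tests undrawn in each arm, unrelated to adherence within the arm. Ordinary missed visits are ignored.

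Scored adherence = true adherence × (1 − *s*)

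| *s* Incentive | *s* Usual Care | Scored Incentive | Scored Usual Care | Difference (points) |
|---|---|---|---|---|
| 0% | 0% | 70% | 55% | +15.0 |
| 25% | 25% | 0.70 × 0.75 = 52.5% | 0.55 × 0.75 = 41.25% | +11.25 |
| 30% | 20% | 0.70 × 0.70 = 49% | 0.55 × 0.80 = 44% | +5.0 |
| 40% | 20% | 0.70 × 0.60 = 42% | 0.55 × 0.80 = 44% | −2.0 |
| 20% | 30% | 0.70 × 0.80 = 56% | 0.55 × 0.70 = 38.5% | +17.5 |

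The true odds ratio is (0.70/0.30) / (0.55/0.45) = 1.91. In the last three rows it reads 1.22, 0.92 and 2.03. With 20% undrawn in Usual Care, the difference vanishes when the Incentive share is 1 − 0.55 × 0.80 / 0.70 = 37%.

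**Effect on power when the arms lose equally.** Assume 100 per arm, a two-sided 5% test and an exchangeable within-person correlation ρ over eight visits, so that the effective number per arm is 100 / [(1 + 7ρ)/8]. With every HRMS tube drawn, power is 94%, 90% and 84% at ρ = 0.30, 0.39 and 0.50. With 20% undrawn in both arms and scored adverse (56% v 44%, odds ratio 1.62), it is 78%, 70% and 62%.

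**Does the no-imputation comparison repair this?** In the first table, yes: the undrawn tests are unrelated to adherence, so it returns 70% v 55% in every row. If they are related to adherence, the percentages are biased:

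- Suppose 30% of adherent and 10% of non-adherent tests are undrawn in both arms. A true 70% reads 0.49 / (0.49 + 0.27) = 64.5%, and a true 55% reads 0.385 / (0.385 + 0.405) = 48.7%. The unadjusted odds ratio is still 1.91, because the selection is the same in both arms.
- Suppose 40% of adherent Incentive tests, 20% of adherent Usual Care tests and 10% of non-adherent tests in both arms are undrawn. The difference is 42% − 44% = −2.0 with adverse scoring. Without imputation it is 0.42/0.69 − 0.44/0.845 = 60.9% − 52.1% = +8.8, against a true +15.

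**The case against.** The strongest reply is that the record rule need not remove the HRMS tube. It names only viral load and CD4, it follows a sentence promising blood every 3 months for primary and secondary outcomes, and HRMS adherence is defined at each 3-month assessment. Staff could properly skip the other two tubes and keep this one. That reading is available, so the documents do not show that every record-based visit lacks an HRMS result. They do not exclude it either, since the words used are about replacing the collection of blood samples. Only the COVID-19 text settles the matter, and there no study draw takes place.

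A reader might also infer that the best-engaged participants are the ones scored non-adherent, and that the Incentive arm loses more. The documents do not support either as a finding. A recent clinic result implies contact with care, but no substitution rate and no link with adherence is given. Nor is it stated that forwarded program results would serve as the medical record. The opposite imbalance would inflate the effect.

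Finally, the plan has safeguards. The no-imputation comparison and the check of missingness by arm would probably expose a material discrepancy. They would not say which estimate to believe, and the plan's only response is tentative conclusions. That is a weak result for a problem that can be prevented at the draw or coded correctly afterwards.

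**Conclusion.** The point holds in a limited form. The imputation rule gives an unjustified value to any HRMS test not drawn by design. This follows directly from the text for remaining assessments under the COVID-19 procedures, though the documents do not say how many there are. It is possible, depending on how the sentence is read, wherever records replace viral load and CD4 sampling.

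On the assumed 70% v 55%, equal loss shrinks the difference (to 11.25 points at 25%). Unequal loss can shrink it further (5.0), reverse it (−2.0) or inflate it (17.5). These sizes rest entirely on assumed adherence and substitution rates. More substitution in the Incentive arm is plausible but not documented. The no-imputation comparison recovers the true percentages only if substitution is unrelated to adherence within each arm. The unadjusted odds ratio also survives if the relation is the same in both arms.

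It would be wrong to read this as a threat to the primary result. It is a correctable weakness in one secondary outcome, and worth correcting because the correction is cheap.

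**What to change.** In Risks, a. Medical risks, state that record values may replace only the viral load and CD4 tubes, and that the planned 5 cc HRMS tube is drawn at every in-person assessment.

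In Missing data, define a separate category, *not assessed*, for HRMS results not drawn by design. It should cover both record substitution and remote assessments under the COVID-19 procedures, since no wording about tubes can recover the latter. Handle these results by multiple imputation or leave them missing, and do not score them as non-adherent. Keep adverse scoring for assessments that the participant missed. Report the number not assessed by arm, so that a reader can judge any imbalance.

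The cost is a sentence or two in each place, one small tube kept at visits where it might have been skipped (within the 25 cc already planned), and a little more analysis work. Multiple imputation or leaving the values missing still rests on an assumption about why tests were undrawn, which should be stated.
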